8.6 Stopping Rules

Monitoring rules are described above in [Section 8.5](#).

For the purposes of stopping rules, Baseline is defined as the average of Day 1 pre-dose assessment and the last measurement prior to Day 1.

8.6.1 *Stopping Rules for Liver Chemistry Elevations*

In the event of confirmed laboratory results meeting any of the following criteria, dosing of a patient with Study Drug will be stopped permanently:

1. ALT or AST > 8 x ULN, which is confirmed
2. ALT or AST > 5 x ULN, which is confirmed and persists for \geq 2 weeks
3. ALT or AST > 3 x ULN (or the greater of 2 x Baseline value or 3 x ULN if the Baseline value was $>$ ULN), which is confirmed and total bilirubin $>$ 2 x ULN or INR $>$ 1.5
4. ALT or AST > 3 x ULN (or the greater of 2 x Baseline value or 3 x ULN if the Baseline value was $>$ ULN), which is confirmed, and the new appearance (i.e., onset coincides

with the changes in hepatic enzymes) of fatigue, nausea, vomiting, right upper quadrant pain or tenderness, fever, rash, or eosinophilia ($>$ ULN) felt by the Investigator to be potentially related to hepatic inflammation

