9.5 Procedures for Handling Special Situations

9.5.1 *Abnormalities of Laboratory Tests*

Clinically-significant abnormal laboratory test results may, in the opinion of the Investigator, constitute or be associated with an AE. Examples of these include abnormal laboratory results that are associated with symptoms, or require treatment, e.g., bleeding due to thrombocytopenia, tetany due to hypocalcemia, or cardiac arrhythmias due to hyperkalemia. Whenever possible, the underlying diagnosis should be listed in preference to abnormal laboratory values as AEs. Clinically-significant abnormalities will be monitored by the Investigator until the parameter returns to its baseline value or until agreement is reached between the Investigator and Sponsor Medical Monitor that monitoring is no longer necessary. Laboratory abnormalities deemed not clinically-significant (NCS) by the Investigator should not be reported as AEs. Similarly, laboratory abnormalities reported as AEs by the Investigator should not be deemed NCS on the laboratory sheet.

The Investigator is responsible for reviewing and signing all laboratory reports. The clinical laboratory reports will serve as source documents and should include the Investigator's assessment of clinical significance of out of range/abnormal laboratory values and signatures.

All platelet count results must be reviewed promptly (within 48 hours of receipt) by the Investigator or the designee to ensure that the count has not met the stopping rule and to determine whether the rate of decline is suggestive that the patient could be approaching the dose interruption rule of 75,000/mm³ as specified in [Section 8.6.3](#).

Any case of a platelet count reduction to levels below 50,000/mm³ is considered an adverse event of special interest and should be reported in an expedited fashion to the Sponsor as per [Sections 9.3.3.1](#) and [9.4.1](#)).

All results of liver function tests must be reviewed promptly (within 48 hours of receipt) by the Investigator or the designee to ensure that the result has not met the stopping rules per [Section 8.6.1](#).

All results of renal function tests must be reviewed promptly (within 48 hours of receipt) by the Investigator or the designee to ensure that the result has not met the stopping rules per [Section 8.6.2](#).

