10.1.3 Safety Endpoints

The safety analysis will be performed using the following parameters:

- AEs
- Vital signs and weight
- Physical examinations
- Clinical laboratory tests (serum chemistry, hematology, coagulation, urinalysis)
- Proportion of patients with platelet drop by severity, including platelet drop below lower limit of normal (LLN), platelet drop greater than 30% from Baseline, or any platelet drop meeting stopping rules.
- Proportion of patients with liver adverse events by severity, number of patients meeting liver stopping rules, and change in liver function tests by severity.
- Proportion of patients with renal adverse events by severity, number of patients meeting renal stopping rules, and change in renal function tests by severity.
- ECGs (including serial ECGs in a subgroup of patients undergoing serial PK sampling)
- Use of concomitant medications

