1.4.4 Safety Endpoints

The safety analysis will be performed using the following parameters:

- Adverse events (AEs)
- Vital signs and weight
- Physical examinations
- Clinical laboratory tests (serum chemistry, hematology, coagulation, urinalysis)
- Proportion of patients with platelet drop by severity, including platelet drop below lower limit of normal (LLN), platelet drop greater than 30% from baseline, or any platelet drop meeting stopping rules.
- Proportion of patients with liver adverse events by severity, number of patients meeting liver stopping rules, and change in liver function tests by severity.
- Proportion of patients with renal adverse events by severity, number of patients meeting renal stopping rules, and change in renal function tests by severity.
- Electrocardiograms (ECGs) (including serial ECGs in a subgroup of patients undergoing serial PK sampling)
- Use of concomitant medications

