The number and percent of patients who stopped treatment because they met a protocol-defined safety monitoring rule(s) and stopping rule(s) (see Protocol Section 8.6 for details) will be tabulated by treatment group. A listing will be provided for patients who met protocol-defined safety monitoring rules and for patients who terminated treatment due to a protocol-defined stopping rule as well.

Additional investigation of abnormalities in liver chemistry, platelet counts, and renal functions will be performed for on-treatment and on-study periods as below.

Abnormalities in liver chemistry: The number and percent of patients falling in each of the following categories (using available central and local laboratory assessments) will be tabulated based on worst post-baseline assessments by treatment group and for pooled ISIS 678354.

- The higher of ALT > 3 x upper limit of normality (ULN) or ALT > 2 x Baseline
- ALT/AST > 3 x ULN
- ALT/AST > 5 x ULN
- ALT/AST > 8 x ULN
- ALT > 3 x ULN - ≤ 5 x ULN
- ALT > 5 x ULN - ≤ 8 x ULN
- Total bilirubin > 2 x ULN
- ALP > 2 x ULN and (baseline ALP < 2 x ULN or baseline ALP missing)

The number and percent of patients falling in each of the following categories based on confirmed worst post-baseline assessments will be tabulated by treatment group and for pooled ISIS 678354.

- ALT/AST > 8 x ULN, which is confirmed
- ALT/AST > 5 x ULN, which is confirmed and persist for at least 2 weeks
- ALT/AST > 3 x ULN (or the greater of 2 x Baseline value or 3 x ULN if the Baseline value was > ULN), which is confirmed and either:
 - Total bilirubin > 2 x ULN, or
 - INR > 1.5, or
 - Temporal association with symptoms of fatigue, nausea, vomiting, right upper quadrant pain or tenderness (PT: abdominal pain or abdominal pain upper), fever, rash, or eosinophilia (PT: Eosinophilia and the corresponding lab value >ULN within the interval of associated Eosinophilia start and end date); and where temporal will be defined as the report date of the confirmed laboratory parameter occurring within the interval of the associated adverse event start and stop dates

For patients having confirmed 3-fold or greater elevations above the ULN for ALT or AST, a listing of all ALT, AST, total bilirubin, INR, and alkaline phosphatase records will be provided.

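### The symptom branch of the SAP's liver stopping-rule table is not Protocol 8.6.1 criterion 4: it tests date overlap, not new onset or Investigator judgement, so its count may not match the protocol rule

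*Combined protocol and SAP*

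**What the plan says.** Protocol 8.6.1, criterion 4, starts from ALT or AST above 3 x ULN (or a baseline-adjusted threshold when Baseline exceeds ULN). It continues "which is confirmed, and the new appearance (i.e., onset coincides", and the bracket goes on to tie that onset to the enzyme changes. The listed symptoms and eosinophilia above ULN must also be "felt by the Investigator to be potentially related to hepatic inflammation".

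SAP 3.7.4 tabulates patients by confirmed worst post-baseline liver values, following the 8.6.1 criteria one by one. For the symptom criterion it uses a temporal association, "defined as the report date of the confirmed laboratory parameter occurring within the interval of the associated adverse event start and stop dates". Eosinophilia is specified as "PT: Eosinophilia and the corresponding lab value >ULN within the interval of associated Eosinophilia start and end date".

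Both documents name the "number of patients meeting liver stopping rules" as part of a safety endpoint (Protocol 10.1.3, SAP 1.4.4). SAP 3.7.4 also plans a separate count of patients who stopped treatment because they met a protocol monitoring or stopping rule, with listings. It does not say which of the two tables reports the endpoint.

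**The concern.** Most of the SAP table copies the protocol thresholds, so a reader will take it as the 8.6.1 count. In the symptom branch, two of the protocol's conditions have gone: that the symptom is new, and that the Investigator suspects the liver. What remains is whether one laboratory date falls inside an adverse event's dates. A symptom that has been open for months passes. A new symptom that is not open on that date fails.

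Confirmed elevations with symptoms are likely to be few, so the table will be read patient by patient. Liver safety is a live question: Protocol 2.3.4 reports treatment-related ALT above 3 x ULN in 2 Phase 1 subjects in the 60 mg every-4-week cohort, which had 6 active subjects. Both had a history of raised ALT, and 60 mg every 4 weeks exceeds every regimen here, so this is context and not an expected rate.

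**Working it through.** There is no planned figure to reproduce; the check is of two definitions.

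**Side by side**

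| Element | Protocol 8.6.1, criterion 4 | SAP 3.7.4, symptom branch |
|---|---|---|
| Enzymes | Confirmed, > 3 x ULN or baseline-adjusted | Same |
| Timing | Symptom is new and starts with the enzyme change | Report date lies within the AE dates |
| Judgement | Investigator suspects hepatic inflammation | Not tested |
| Eosinophilia | New, above ULN, same judgement | AE with that preferred term, plus laboratory value above ULN within its dates |

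**As logical tests.** Let N = new onset with the enzyme change, J = Investigator's judgement, A = an AE recorded under the required term, S and T = AE start and stop, R = report date, E = eosinophils above ULN (eosinophilia cases only).

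- Protocol met = N and J (and E)
- SAP met = A and S ≤ R ≤ T (and E)

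Six invented patients follow, all with a confirmed elevation, the sample collected on day 60 and R = 62. The 2-day lag is the limit Protocol 6.2.1 sets for laboratory alerts.

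| Case | SAP test | SAP | Protocol |
|---|---|---|---|
| 1. Fatigue, day -10 to 200, judged unrelated | -10 ≤ 62 ≤ 200 | yes | no |
| 2. New nausea, day 58 to 61, judged hepatic | 62 ≤ 61 fails | no | yes |
| 3. New vomiting, day 63 to 70, judged hepatic | 63 ≤ 62 fails | no | yes |
| 4. New eosinophils > ULN, judged hepatic, recorded under another term | A fails | no | yes |
| 5. Eosinophilia AE, day 58 to 70, value > ULN, new, judged hepatic | 58 ≤ 62 ≤ 70 | yes | yes |
| 6. New rash, day 59 to 75, judged hepatic | 59 ≤ 62 ≤ 75 | yes | yes |

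The rules disagree in 4 of 6 cases: one over-count and three under-counts. The cases were chosen to exercise each condition, so 4 of 6 is not a rate.

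**How firm each direction is.** Case 1 holds for any R from day -10 to day 200. Protocol 9.4.2 records AEs from consent, so such an AE can exist. If the table were restricted to treatment-emergent events, fatigue starting on day 10 would give the same result.

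Cases 2 and 3 depend on which value supplies R. Under SAP 3.7.4 the initial value stands if the retest is the same or worse, or if there is no retest within 7 days; a better retest replaces it. Case 2 would count if R fell on days 58 to 61. Case 3 would count if a later confirmed value, reported on days 63 to 70, were also tested. The SAP does not say whether every confirmed value is tested or only the worst.

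Case 4 is plausible because Protocol 9.4 asks for signs and symptoms to be grouped under one diagnosis, and 9.5.1 prefers a diagnosis to a laboratory term.

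**Date handling.** SAP 3.7.1.1 sets a wholly missing AE start to the first dose, which stretches the interval back to Day 1. End dates are imputed only for resolved events, and the SAP does not say how an ongoing symptom meets a test that needs a stop date. SAP 3.7.2 opens a new record when severity changes, so a record's start date need not be the symptom's first onset.

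**Scale.** Active patients per regimen: 25 x 4/5 = 20. Pooled active: 4 x 20 = 80. One misclassified patient is 1/20 = 5.0 percentage points of a regimen group, or 1/80 = 1.25 points of the pooled active group.

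**The case against.** The strongest reply is that the SAP already has a protocol-based count. Protocol 8.5 and 8.8 require permanent discontinuation once a stopping criterion is met and confirmed, so the table of patients stopped under Protocol 8.6 should hold nearly every on-treatment case, with the Investigator's judgement built in. The criticised item sits under additional investigation of abnormalities and is never said to report the endpoint. An opinion cannot be programmed from dates, so some proxy is unavoidable. The table also drives no treatment decision, and AE and liver listings allow case review.

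Much of this stands. But the stopped-treatment table omits patients who met the rule without being stopped, and those who met it after their last dose. The endpoint concerns meeting the rule. A proxy is acceptable if it is labelled as one, yet new onset can be tested from dates and is left out.

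On eosinophilia, a reader might infer that the protocol needs only the laboratory finding, and that the 9.5.1 rule, "Laboratory abnormalities deemed not clinically-significant (NCS) by the Investigator should not be reported as AEs", would hide qualifying cases. The text does not support this. The Investigator's judgement applies to eosinophilia too, and a count judged not clinically significant is unlikely to be one linked to hepatic inflammation. Requiring an AE is thus a fair proxy for that judgement; the remaining gap is an event recorded under another term.

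**Conclusion.** The point holds in a limited form. The symptom branch of SAP 3.7.4 does not implement Protocol 8.6.1 criterion 4 and can err in both directions. The over-count follows directly from the stated overlap rule. The under-count from timing depends on which value's report date is used, which the SAP leaves open.

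Three stronger readings are not supported:

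- That the count is bound to disagree with 8.6.1. Errors in opposite directions can cancel, and both counts could be zero.
- That a number of misclassified patients, or a share of missed cases, can be predicted. The documents give neither the frequency of confirmed elevations nor that of concurrent symptoms.
- That the whole liver table is wrong. The other branches use the protocol's thresholds.

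The size that can be stated is the 5.0 or 1.25 percentage points per misclassified patient, assuming the planned cohort sizes are reached. It is worth correcting because the endpoint is named in both documents and the data needed are already collected.

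**What to change.** Change the SAP only; the clinical rule in Protocol 8.6.1 stays as it is.

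- In 3.7.4, require the first onset of the symptom AE to coincide with the ALT/AST elevation. Link records split by a severity change so that the earliest start is used.
- Use sample collection dates. Prespecify the window around the elevation and label it a convention. If 7 days is borrowed from the SAP's confirmation rule, say that it is a laboratory retest interval with no protocol standing as a symptom window. End the elevation by the same baseline-adjusted threshold as 8.6.1.
- State which confirmed values are tested, and how ongoing AEs and missing AE dates are treated.
- Show laboratory eosinophils above ULN without an AE as a separate flagged line. Counting them as meeting the rule would drop the Investigator's judgement and depart from 8.6.1.
- Place the existing count of patients stopped under Protocol 8.6 beside this table, name the table that reports the endpoint, and label the programmed one an algorithmic screen.

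The cost is SAP wording and some programming. AE dates, collection dates and eosinophil counts (haematology every 14 days on treatment) are already collected. The downside is that the window remains a convention and the Investigator's judgement still cannot be programmed.

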Age will be presented in years. Weight will be presented in kg. Height will be presented in cm. Temperature will be presented in °C. Laboratory listings will be presented using original unit. Summary tables of lab results will be based on original unit. For multiple original units within the parameters, the results will be converted to the majority of units as reported. Lab shift tables and abnormalities tables will be based on mock shell displays.

The lab data will be reported using central lab and/or local lab depending on the type of outputs or values. [Table 2](#) and [Table 3](#) outline which data source, lab unit and visits should be used for the specific outputs and values.

Table 2: Summary of Lab Data Source per Type of outputs

	Type of Outputs	Data source	Unit	Visits
--	-----------------	-------------	------	--------

Listings	Listings of lab data	Central and local lab in separate listings	Original Unit	SCH + USCH visits
Tables, Figures	All efficacy endpoints (primary, secondary, exploratory)	Central lab	Original Unit	analysis SCH + USCH within visit window
	Descriptive summary of platelet count data	Central and local lab, separate tables and figures	Original Unit (cells/mm ³)	nominal SCH visits
	Descriptive summary safety lab data other than platelet counts	Central lab	Original Unit	nominal SCH visits
	Safety shift tables	Central and local lab	Per mock shells	nominal SCH + USCH visits
	Abnormalities lab tables	Central and local lab	Per mock shells	nominal SCH + USCH visits

SCH: scheduled; USCH: unscheduled

Table 3: Summary of Lab Data Source per Type of Values

Type of values	Data source	Unit	Visits
Baseline for platelet count	Central and local lab	Original Unit (cells/mm ³)	SCH + USCH visits prior to the first dose of Study Drug
Baseline for other safety labs	Central lab	Original Unit	nominal based on SCH + USCH visits; selected as last non missing prior to first dose of Study Drug
Confirmed lab value	Central and local lab	Per mock shells	nominal SCH + USCH visits

SCH: scheduled; USCH: unscheduled

Efficacy assessments (i.e. lipid panel) will be mapped to an analysis visit per the analysis visit windows as specified in [Appendix A](#) and summarized by analysis visit. The selection rule of analysis visits is specified in [Appendix A](#) as well.

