Safety assessments will be summarized by nominal visit as collected in CRF. For summary tables by nominal visit, only scheduled visits will be used. For multiple records at the nominal (scheduled) visit, the average will be used for continuous values, or the worst will be used for categorical values.

For summary tables of platelet counts by nominal visit, scheduled visits from central lab data and separately, from local lab data will be used. For multiple records at the nominal (scheduled) visit, the average will be used for continuous values, or the worst will be used for categorical values.

3.2.2 *Patient Population Analyzed*

The following analysis sets will be used for the analysis of data as described within each analysis set.

Screened Patients are defined as the patients who sign an informed consent form.

Randomized Patients are defined as the patients who receive a randomization assignment.

Full Analysis Set (FAS): All patients who are randomized and received at least 1 dose of Study Drug (ISIS 678354 or placebo). The FAS represents the practically-feasible intent-to-treat (ITT) population as delineated in International Conference on Harmonisation (ICH) Guideline E9. This population will be used for the analysis of efficacy.

Per Protocol Set (PPS): Subset of the FAS who received prior to the Primary Analysis Timepoint at least 5 monthly doses of Study Drug for patients randomized in Cohorts A and B, or at least 11 every 2-week doses for patients randomized in Cohort C, or at least 22 weekly doses for patients randomized in Cohort D, and who have no major protocol deviations that could compromise the interpretation of efficacy. Major deviations will be determined prior to unblinding for statistical analysis. This population will be used for supportive inferences concerning efficacy.

Safety Set (SS): All patients who are randomized and received at least 1 dose of Study Drug. This population will be used for all safety analyses.

PK Population: All patients who are randomized and received at least 1 dose of ISIS 678354, and have at least 1 evaluable concentration result post first dose. This population will be used for analysis of PK data.

PK Subgroup: A subset of PK population who will undergo additional PK sampling after dose administration on Day 1 and Week 21 (Cohorts A and B) / Week 25 (Cohorts C and D) to evaluate the plasma PK parameters of ISIS 678354.

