Abnormalities of platelet counts: The number and percentage of patients falling in each of the following categories (using available central and local laboratory assessments) based on worst post-baseline assessments will be provided:

- Any 2 occurrences of platelet count < 140,000 cells/mm³
- Any single occurrence of platelet count < 100,000 cells/mm³
- Any 2 occurrences of platelet count < 140,000 cells/mm³ or any single occurrence of value < 100,000 cells/mm³

The nadir platelet count will be summarized by following categories:

- Decrease \geq 30% from baseline
- Decrease \geq 50% from baseline
- 100,000 cells/mm³ to < 140,000 cells/mm³
- 75,000 cells/mm³ to < 100,000 cells/mm³
- 50,000 cells/mm³ to < 75,000 cells/mm³
- 25,000 cells/mm³ to < 50,000 cells/mm³
- 0 to < 25,000 cells/mm³

All categories of abnormalities in platelet count will be summarized based on confirmed values for on-study period as well.

Abnormalities of renal function: The number and percentage of patients falling in each of the following categories (using available central and local laboratory assessments) based on confirmed worst post-baseline assessments will be provided:

- eGFR by CKD-EPI $>$ 25% decrease from baseline
- UACR $>$ 250 mg/g
- UPCR $>$ 0.5 g/g
- Serum creatinine increase of $>$ 0.3 mg/dL from baseline

3.7.5 12-Lead Electrocardiogram

ECGs will be performed in triplicate at the visits indicated in the Protocol Appendix A. Patients in PK Subgroup will have additional ECG conducted during the treatment period. Patients determined to have a pacemaker rhythm will be excluded from summary tables.

The ECG data include ventricular rate, PR interval, QRS duration, QT and corrected QT intervals. For the continuous variables, the average of measurements at a given visit will be used for analysis. For the continuous variables above, descriptive statistics (n, mean, standard error, standard deviation, median, P25, P75, minimum, maximum, and mean 95% CI) of the observed values, as well as the change from baseline to each nominal study visit, will be presented by treatment group and for pooled placebo in summary tables. The summary table will be presented in SS and in PK Subgroup separately. Scheduled visits will be used for all summary tables.

The number and percent of patients who have the following reported events will be tabulated by treatment group and for pooled ISIS 678354.

- Absolute QT/QTcF/QTcB $>$ 450 msec
- Absolute QT/QTcF/QTcB $>$ 480 msec

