- Absolute QT/QTcF/QTcB >500 msec
- Increase from baseline in QT/QTcF/QTcB >30 msec
- Increase from baseline in QT/QTcF/QTcB >60 msec
- Increase from baseline in PR \geq 50% (if absolute baseline <200 msec)
- Increase from baseline in PR \geq 25% (if absolute baseline >200 msec)
- Increase from baseline in QRS \geq 50% (if absolute baseline <100 msec)
- Increase from baseline in QRS \geq 25% (if absolute baseline >100 msec)

QTcB (msec) = QT (msec) / (RR)^{1/2}; if RR is missing, use QT (msec) * (HR(bpm)/60)^{1/2}

QTcF (msec) = QT (msec) / (RR)^{1/3}; if RR is missing, use QT (msec) * (HR(bpm)/60)^{1/3}

All the ECG data with scheduled and unscheduled visits will be listed.

An exploratory exposure-response analysis will be performed in PK-ECG Set to evaluate the relationship between QTcF and plasma concentration of ISIS 678354. The relationship between ISIS 678354 concentration and change from baseline QTcF (Δ QTcF) and placebo-corrected change from baseline QTcF ($\Delta\Delta$ QTcF) will be investigated using a linear mixed-effects modeling approach on time-matched ECG and ISIS 678354 concentration data.

Δ QTcF or $\Delta\Delta$ QTcF = $\alpha + \beta_1 \times [\text{ISIS 678354 concentration}] + \beta_2 \times [\text{baseline QTcF}] + \gamma \times [\text{patient effect}]$

$\Delta\Delta$ QTcF = (Δ QTcF for ISIS 678354 treated patient) – (mean of Δ QTcF for pooled placebo group).

Matching of ECG and ISIS 678354 concentration (PK) data will be based on the following algorithm, in the sequence provided:

1. Time of ECG and PK must be within 60 minutes (\pm 60 minutes) of each other.
2. If there are multiple records within the 60 minutes range, the closest match will be chosen.
3. If there is more than one closest match identified in the previous step, the recorded pair with the ECG time point after the PK time point will be chosen.

Plots of Δ QTcF or $\Delta\Delta$ QTcF versus ISIS 678354 concentration including all patients in PK-ECG Set will be generated.

3.8 *Interim Analysis*

There is no interim analysis planned for the study.

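### Read literally, SAP 3.7.5 keeps unscheduled ECGs out of the patient-level outlier counts, whereas the SAP's laboratory abnormality tables include unscheduled results

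*Combined protocol and SAP*

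**What the plan says.** SAP 3.7.5 plans two kinds of ECG table. The first gives descriptive statistics for ventricular rate and the ECG intervals at each nominal visit, in the Safety Set and separately in the PK Subgroup. That paragraph ends: "Scheduled visits will be used for all summary tables".

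The second is a patient-level table, introduced immediately afterwards: "The number and percent of patients who have the following reported events will be tabulated by treatment group and for pooled ISIS 678354". Its rows are absolute QT/QTcF/QTcB above 450, 480 and 500 msec, rises above 30 and 60 msec, and relative increases in PR and QRS. The most serious QT rows are "Absolute QT/QTcF/QTcB >500 msec" and "Increase from baseline in QT/QTcF/QTcB >60 msec". Nothing in this part says which visits feed the table.

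Unscheduled ECGs appear once, after the row definitions: "All the ECG data with scheduled and unscheduled visits will be listed".

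For laboratory data, SAP 3.2.2 (Reporting Conventions), Table 2, is explicit. Descriptive summaries use scheduled visits, while shift tables and abnormality tables use "nominal SCH + USCH visits". Table 2 has no ECG row.

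**The concern.** A by-visit mean and an outlier count ask different questions. Restricting the mean to scheduled visits is sensible, because it keeps timing comparable across patients. The outlier table asks whether a patient ever crossed a limit, and for that every valid post-baseline record matters. Applying the scheduled-only sentence to both would drop some crossings from the table in which readers look for notable ECG changes by dose.

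Safety is part of the primary objective, and ECG is a named safety endpoint (protocol 10.1.3, SAP 1.4.4). Protocol 3.4 foresees additional visits for adverse events or abnormal results, and an ECG taken at such a visit could hold the extreme value. For the rarest row, above 500 msec, a single patient can decide whether the table shows zero.

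**Working it through.** There is no planned figure to reproduce. The check compares the relevant texts, then sets the scale.

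**1. Does the scheduled-only sentence reach the outlier table?**

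- For the broad reading: the sentence covers *all* summary tables. The same section uses the term generally when it says "Patients determined to have a pacemaker rhythm will be excluded from summary tables". If the outlier table were not a summary table, no rule would remove paced patients from its QRS and QTc rows. SAP 3.7.2 also calls its count-and-percent adverse event tables summary tables.
- For the narrow reading: the sentence closes the paragraph on by-visit statistics. The general rule in SAP 3.2.2 is tied to visit: "For summary tables by nominal visit, only scheduled visits will be used". SAP 3.2.4 names the ECG summary over time and the abnormal ECG parameters table as separate outputs.
- Neither side is decisive. No other place in the SAP brings unscheduled ECGs into the outlier table.

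**2. What happens to a patient under the literal reading?**

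Take a hypothetical patient whose highest scheduled QTcF is 470 msec and who has one unscheduled reading of 512 msec.

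- Rows above 480 and above 500: 470 does not exceed 480, so the patient counts in neither. With the unscheduled ECG the patient counts in both.
- Row for a rise above 60, with baseline b: the unscheduled value qualifies if 512 − b > 60, so b < 452. The highest scheduled value qualifies only if 470 − b > 60, so b < 410. The rise goes uncounted when 410 ≤ b < 452.

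**3. Direction.** Adding records, each kept as its own assessment, can raise a patient's worst value or leave it alone. The default denominator is the Safety Set (SAP 3.7), which does not depend on visit type. So leaving records out can only lower each count or leave it unchanged.

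**4. Scale.** Each cohort has 25 patients randomized 4:1.

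- Active per cohort: 25 × 4/5 = 20. One patient is 1/20 = 5 percentage points.
- Pooled active: 4 × 20 = 80. One patient is 1/80 = 1.25 points.
- Pooled placebo: 4 × 5 = 20. One patient is again 5 points.

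These are the weights of one patient, not expected effects.

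**5. Scheduled coverage.** Up to the primary time point, protocol 6.2.3 schedules on-treatment ECGs at Weeks 5, 13, 21 and 25, plus Week 27 in Cohorts C and D. The longest gaps are 13 − 5 = 8 and 21 − 13 = 8 weeks. The PK Subgroup's extra ECGs are scheduled and therefore counted, but they fall in Week 1 and in Week 21 or 25 (SAP Table 4), outside those gaps.

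**The case against.** The strongest reply is that the sentence was meant for the by-visit table only. It follows directly on the statement that this table is produced for both the Safety Set and the PK Subgroup, so *all* may mean both versions. The laboratory rules show that the sponsor separates descriptive from abnormality tables. This stands as a possible reading, and a reader should not infer that exclusion from the outlier counts is an established decision. Two programmers could produce different tables from this text, and either way the same clarification is needed.

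A reader might also infer that such a value disappears from the trial report. It does not. It remains in the ECG listing, and an event that is clinically significant or symptomatic can meet the adverse event definition (protocol 9.3.1) and enter the treatment-emergent tables, which do not depend on visit type. What is lost is the count in this one table.

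A third tempting inference is that the outlier table will be biased downward, most of all in the active arms. The documents do not support that. They give no frequency of unscheduled ECGs, and protocol 8.5 and 8.6 contain no ECG retest rule that would generate them. Protocol 2.3.3 reports no ECG effect in monkeys, and 2.3.4 no clinically significant ECG change in Phase 1. An imbalance would arise only if one arm had more unscheduled ECGs that alone held the crossing.

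Finally, unscheduled ECGs may not be triplicate, and they are taken because of events, so including them mixes measurement quality and makes ascertainment depend on events. That is a real but small cost, which disclosure can handle.

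**Conclusion.** The point holds as a gap between wording and purpose. The literal text of SAP 3.7.5 leaves threshold crossings seen only on unscheduled ECGs out of the outlier counts, nothing elsewhere restores them, and the SAP takes the opposite course for laboratory abnormalities. The effect on any count is zero or downward. Its size cannot be estimated from the documents and may be nil. The conclusion rests on reading *all summary tables* to include the outlier table, which the pacemaker sentence supports and the paragraph placement puts in some doubt. Loss of data and a demonstrated bias between arms are not part of the conclusion. The correction is worth making because it is specific, follows the sponsor's own convention and costs very little.

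**What to change.** In SAP 3.7.5, limit the scheduled-only sentence to the by-visit descriptive ECG tables. Then state that the ECG outlier table uses each patient's worst post-baseline value from scheduled and unscheduled ECGs, taking the visit average where replicates exist. Say in the same place that the pacemaker exclusion applies to both kinds of table. Add a footnote identifying patients whose qualifying value comes only from an unscheduled or non-triplicate ECG, so that readers can see the count with and without them.

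The cost is a few lines of text, one changed programming filter and a footnote. The unscheduled ECGs are already to be listed, so no new data are needed. The rule applies alike to every arm and touches no efficacy analysis.
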